4.3.2.1. Baseline (Randomization) Visit

Subjects are to return to the study site for the Baseline (Randomization) Visit, which must be completed in person. Subjects who continue to meet all study entry criteria may be randomized in the RTSM system and entered into the DBT Phase.

At the Baseline Visit, subjects will be randomized 1:1 across 2 treatment groups: blinded rimegepant 75 mg (n = 300) or matching placebo for rimegepant 75 mg (n = 300). Randomization will be stratified by history of clinically relevant CV disease (yes or no; see [Section 7.1.6](#)). In addition, randomization of subjects in the CV subgroup (“yes” category) will be capped at 15%.

4.3.2.2. DBT EOT Visit

Subjects will return to the study site within 7 (+2) days after administration of double-blind study drug, for review of the eDiary data, assessment of medication compliance, and monitoring of tolerability and safety (including vital signs, laboratory tests, and ECG). If a subject does NOT have a qualifying migraine attack (see [Section 4.1](#)) within 45 days after randomization, they still are required to complete all DBT EOT Visit procedures including assessment of medication compliance and monitoring of tolerability and safety (including vital signs, laboratory tests, and ECG). Subjects who do not have a qualifying migraine attack (see [Section 4.1](#)) during the 45-day DBT Phase will not be eligible for the OLE Phase.

At the DBT EOT Visit, the subject will return the eDiary for review and all study drug, including wallets with used or unused study drug. Subjects will also be evaluated at this visit for entry into the 12-week OLE Phase following laboratory results within acceptable ranges per protocol (see [Table 2](#)). Subjects in the DBT Phase who demonstrate poor compliance will be discussed with the Sponsor, corrective training will be completed by the site with the subject prior to the OLE Phase (see [Sections 6.6](#) and [7.3](#)).

4.3.3. Open-label Extension Phase

4.3.3.1. OLE Eligibility Confirmation Phone Visit

Study eligibility must be confirmed by DBT EOT Visit laboratory results prior to the first dose of open-label rimegepant. The site must contact the subject by phone to confirm OLE Phase eligibility prior to subject taking the first dose of open-label rimegepant.

4.3.3.2. OLE Day 1

Day 1 of the OLE Phase is the same day as the DBT EOT Visit. Sites are to instruct subjects to refrain from dosing with open-label study drug until they have received a phone call from the site confirming their eligibility to enter the OLE Phase.

4.3.3.3. OLE Week 12 / OLE EOT Visit

The OLE Phase will last 12 weeks from the DBT EOT Visit through the OLE Week 12 / OLE EOT Visit.

In the OLE Phase, subjects will be able to take up to 1 tablet of open-label study drug (75 mg ODT rimegepant) per calendar day as needed for acute treatment of migraine of moderate or severe headache pain intensity for a maximum of 18 doses per month (month is 28 days).

- ***During the OLE Phase***

- Subjects are to use open-label study drug as the first treatment for migraine attacks of moderate or severe headache pain intensity, and should not take acute migraine medication before taking open-label study drug (see [Section 16.3](#), [Appendix 3](#)).
- In association with each of the ***First 5 Qualifying Migraine Attacks*** (see [Section 4.1](#)), subjects are required to complete the MQoL Questionnaire within the eDiary at 24 hours after dosing with open-label study drug. In the event an MQoL Questionnaire is not completed for any of the first 5 qualifying migraine attacks (eg, inadvertently missed), MQoL Questionnaires will be collected for subsequent qualifying migraine attacks until a total of 5 MQoL Questionnaires are completed.
- If migraine-associated symptoms persist beyond 2 hours after dosing with open-label study drug, subjects may use permitted acute migraine medication (see [Section 16.3](#), [Appendix 3](#)) for the purposes of rescue, as needed and in accordance with the standard of care. *All dosing of rescue medication (permitted or exclusionary), as defined in [Section 6.4.4](#), is to be recorded on the Rescue Medication paper diary.*

Subjects will record the following about their migraine attacks in the eDiary:

- migraine occurrence (yes, no);
- migraine headache pain intensity (mild, moderate, severe);
- study drug dosing (yes, no);
- Migraine Quality of Life Questionnaire (MQoL) at 24 hours postdose (until 5 are completed)

Subjects will continue to record all concomitant medications, including acute migraine medications (*used for non-rescue purposes only*, see [Section 5.5.2](#)) and standard prophylactic migraine medications (see [Section 16.2](#), [Appendix 2](#)) taken during the OLE Phase in the Concomitant Medication paper diary.

Subjects will return to the study site at the OLE Week 12 / OLE EOT Visit (OLE Day 85 +2 days) for assessment of medication compliance and assessment of tolerability and safety (including vital signs, laboratory tests, and electrocardiography) ([Table 2](#)). Subjects must return the eDiary, unused study drug to the study site at each visit.

All subjects *who discontinue early from the OLE Phase* are to complete the OLE Week 12 / EOT Visit (see [Table 2](#)).

In the event that the feasibility of study visits is impacted due to COVID-19, some selected study visits may be conducted remotely (Ex: Telephone, telemedicine) and must be documented within the source records as being conducted remotely. All procedures not able to be completed due to a visit being conducted remotely must be reported as a protocol deviation and can be performed at the next visit, where appropriate to do so based on subject participation. During the OLE Phase, the following visits may be completed remotely due to COVID-19: Week 2, Week 4, Week 8 and the Follow-up Week 2 Visit. The following visits must be completed in-person: Week 12/ EOT Visit.

4.3.4. Follow-up Phase

The Follow-up Phase will have 1 scheduled visit at Follow-up Week 2, which will occur approximately 2 weeks (14 days +/- 2 days) after the OLE Week 12 / EOT Visit. Subjects will return to the study site to collect vital signs, assessment of AEs/SAEs, and to have a urine pregnancy test performed (WOCBP). Investigators are to assess subjects for AEs consistent with drug dependency or withdrawal effects and report as appropriate (see [Section 7.4](#)).

All subjects who enter the OLE Phase are to complete the Follow-up Week 2 Visit (regardless of completing the OLE Phase), except those who discontinue early from the OLE Phase due to withdrawal by subject or lost to follow-up.

Subjects will continue to record all concomitant medications, including acute migraine medications (used for non-rescue purposes only, see [Section 5.5.2](#)) and standard prophylactic migraine medications (see [Section 16.2](#), [Appendix 2](#)), taken during the Follow-up Phase in the Concomitant Medication paper diary.

4.4. Post Study Access to Therapy

At the end of the study, the Sponsor will not continue to supply study drug to subjects or investigators. The Investigator is to ensure that the subject receives permitted acute migraine standard of care medication used to treat the condition under study.

5. POPULATION

Individuals entered in this trial will be subjects who suffer from migraine attacks. The treatment setting for these subjects may include clinics, institutions, or private office practices. Subjects may be recruited through a variety of sources, including referrals from physicians and other health care professionals.

5.1. Number of Subjects

It is anticipated that approximately 900 subjects will be screened in order to randomize approximately 600 subjects. The subjects will be randomized in a 1:1 ratio to blinded rimegepant or matching placebo during the Double-blind Treatment (DBT) Phase. It is

estimated that approximately 510 subjects will be entered into the Open-label Extension (OLE) Phase.

5.2. Inclusion Criteria

1. Target Population

Minimum 1 year documented history of migraine attacks (with or without aura) consistent with a diagnosis according to the International Classification of Headache Disorders, 3rd Edition.⁸

Per self-report, with confirmation from Investigator / supporting medication record, subjects must have:

- a. Migraine attacks present for more than 1 year with the age of onset prior to 50 years of age.
- b. Migraine attacks, on average, lasting about 4 - 72 hours if untreated.
- c. 4 to 14 migraine days (see [Section 6.4.5](#)) per month on average across the 3 months prior to the Screening Visit (month is defined as 28 days for the purpose of this protocol).
- d. Subjects must be able to distinguish migraine attacks from tension headaches.
- e. Subjects on prophylactic migraine medication (excluding CGRP antagonists) are permitted to remain on therapy if they have been on a stable dose for at least 3 months (12 weeks) prior to the Screening Visit, and if the dose is not expected to change during the course of the study.

2. Triptan unsuitable (see [Appendix 4](#)).

3. Age and Reproductive Status

- a. Subjects ≥ 18 years of age.
- b. Subject meets reproductive criteria. Refer to [Appendix 5](#) for reproductive criteria for female ([Section 16.5.1](#)) subjects.
- c. At the Baseline Visit prior to dispensing investigational study drug, WOCBP must have a negative urine pregnancy test (minimum sensitivity 25 IU/L or equivalent units of HCG).

4. Subjects must be able to fully comply with the prohibitions and restrictions on the concomitant use of medications and therapies (including moderate to strong inhibitors and inducers of the CYP3A4 enzyme and strong inhibitors of the P-gp transporter) detailed in [Section 16.1](#), [Appendix 1](#).

5. For Germany only: Written informed consent must be obtained from the subject in accordance with requirements of the study center's institutional review board (IRB) or ethics committee and in accordance with local regulations, prior to the initiation of any protocol-required procedures (as described in [Section 10.5](#)); refer to [Section 16.7.2](#).

5.3. Exclusion Criteria

1. Target Disease Exclusion:

- a. History of cluster headache, basilar migraine (migraine with brainstem aura), or hemiplegic migraine
- b. Current Medication-overuse headaches
- c. Headaches occurring 15 or more days per month (migraine or non-migraine) in any of the 3 months prior to the Screening Visit
- d. 7 or more non-migraine headache days per month, on-average, across the 3-months prior to the Screening Visit

2. History and Concurrent Diseases

- a. History of gastric, or small intestinal surgery (including Gastric Bypass, Gastric Banding, Gastric Sleeve, Gastric Balloon, etc.), or other disease or condition (e.g. chronic pancreatitis, ulcerative colitis, etc.) that causes malabsorption
- b. Body mass index ≥ 35 kg/m²
- c. History of, treatment for, or evidence of, alcohol or drug abuse within the past 12 months or subjects who have met DSM-V criteria⁹ for any significant substance use disorder within the past 12 months prior to the Screening Visit
- d. Current diagnosis of schizophrenia, bipolar, or borderline personality disorder
- e. History or current evidence of other major psychiatric disorder that might interfere with the ability to properly report clinical outcomes
- f. Major depressive (MDD) or any anxiety disorder (AD) which requires more than 1 daily medication for each disorder, or major depressive episode (MDE) within last 12 months. Medications to treat major depressive disorder or an anxiety disorder must have been at a stable dose for ≥ 3 months (12 weeks) prior to the Screening Visit
- g. Active chronic pain syndrome (such as fibromyalgia, chronic pelvic pain, complex regional pain syndrome [CRPS])

- h. Other pain syndromes (including trigeminal neuralgia), dementia, or significant neurological disorders (other than migraine) that, in the Investigator's opinion, interfere with study assessments of safety or efficacy
- i. Current diagnosis of major depressive disorder requiring treatment with atypical antipsychotics, schizophrenia, bipolar disorder, or borderline personality
- j. History with current evidence of uncontrolled, unstable or recently diagnosed cardiovascular disease (including, but not limited to: ischemic heart disease, coronary artery vasospasm, myocardial infarction [MI], acute coronary syndrome [ACS], percutaneous coronary intervention [PCI], cardiac surgery), cerebral ischemia (including, but not limited to: stroke or transient ischemic attack [TIA]) during the 6 months (24 weeks) prior to the Screening Visit
- k. Systolic blood pressure >150 mmHg or diastolic blood pressure >100 mmHg after 10 minutes of rest. This may be repeated once at the Screening Visit to confirm reproducibility.
- l. History or current evidence of any unstable medical conditions (e.g. history of congenital heart disease, arrhythmia or cancer)
- m. Positive drug screen for drugs of abuse that in the investigator's judgment is medically significant, in that it would impact the safety of the subject or the interpretation of the study results

In addition:

- i. Detectable levels of cocaine, amphetamine, and phencyclidine (PCP) in the drug screen are exclusionary. Retesting is not allowed.
- ii. Subjects who test positive for amphetamines, and who are on a prescribed amphetamine medication for an approved indication (e.g. ADHD) will be allowed into the study at the Investigator's discretion. This determination by the Investigator must be well documented in the subject's source medical records. The stimulant dose must be stable from 3 months (12 weeks) prior to Baseline Visit until the OLE Week 12 or OLE EOT Visit occurs.
- iii. Detectable levels of marijuana in the drug screen are not exclusionary, if in the Investigator's documented opinion the subject does not meet DSM-V criteria⁹ for substance use disorder, and the positive test does not signal a clinical condition that would impact the safety of the subject or interpretation of the study results. Subject must agree to refrain from marijuana use during the study.

3. Allergies and Adverse Drug Reactions

- a. History of drug or other allergy which, in the opinion of the investigator, makes the subject unsuitable for participation in the study. “Rimegepant is contraindicated in subjects with a hypersensitivity to any component of its formulation.”

4. Sex and Reproductive Status

- a. WOCBP who are unwilling or unable to use required contraception (Refer to [Section 16.5 Appendix 5](#) for Contraceptive and Barrier Guidance).
- b. Women who are pregnant, lactating or breastfeeding
- c. Women with a positive pregnancy test at the Screening Visit or prior to study drug administration

5. ECG and Laboratory Test Findings

- a. Any clinically significant abnormality identified on the medical, ECG or laboratory evaluation. A subject with a clinical abnormality or laboratory parameters outside the reference range may be included only if the Investigator considers the finding not clinically significant, that it will not introduce additional risk, nor interfere with the study procedures (not including exclusion criteria listed in [Section 5.3](#)).
- b. Estimated glomerular filtration rate (eGFR) according to the re-expressed abbreviated (four-variable) Modification of Diet in Renal Disease (MDRD) Study equation <30 ml/min/1.73m².
- c. Total bilirubin >1.5 x ULN (For Gilbert’s syndrome, direct bilirubin $>ULN$ is exclusionary).
- d. AST or ALT >2 x ULN.
- e. Serum albumin <2.8 g/dL
- f. Neutrophil count $\leq 1000/\mu\text{L}$ (or equivalent)
- g. HbA1c $>7.5\%$
- h. Evidence of organ dysfunction or any clinically significant deviation from normal on physical examination, vital signs, 12-lead electrocardiogram (ECG), or clinical laboratory determinations beyond what is consistent with the target population.

6. Prohibited Medications and Devices

- a. Non-Narcotic Analgesics (e.g., nonsteroidal anti-inflammatory drugs [NSAIDs], paracetamol [acetaminophen], gabapentin, etc.) taken ≥ 15 days per month for a non-headache indication during the 3 months (12 weeks) prior to the Screening Visit

- b. Other CGRP antagonists (beyond rimegepant), including:
 - i. CGRP antagonist monoclonal antibodies taken within 6 months (24 weeks) prior to the Screening Visit
 - ii. CGRP antagonist small molecules taken within 10 days prior to the Screening Visit
- c. Botulinum toxin injections (e.g., Botox®) used for the prevention of migraine taken within 3 months (12 weeks) prior to the Screening Visit
- d. Cefaly™ or any other device for migraine treatment or prevention used within 3 months (12 weeks) prior to the Screening Visit
- e. Ergotamine taken ≥ 10 days per month on a regular basis for ≥ 3 months (≥ 12 weeks) in the year prior to the Screening Visit
- f. Narcotics, such as opioids (e.g., morphine, codeine, oxycodone, hydrocodone) or barbiturates (e.g., butalbital) taken ≥ 4 days per month during the 3 months (12 weeks) prior to the Screening Visit
- g. Permitted acute migraine medication taken ≥ 15 days per month for a non-headache indication during the 3 months (12 weeks) prior to the Screening Visit (see [Section 5.5.2](#))

7. Other Exclusion Criteria:

- a. For France and Germany only: Persons deprived of their liberty by a judicial or administrative decision. (Refer to [Section 16.7](#) for France and Germany)
- b. For France and Germany only: Adults subject to a legal protection measure (guardianship, curatorship, and safeguard of justice). (Refer to [Section 16.7](#) for France and Germany)
- c. For France only: Persons not affiliated to a social security scheme or equivalent. (Refer to [Section 16.7](#) For France)
- d. Exposure to non-biological investigational agents within 30 days prior to the Screening Visit
- e. Exposure to biological investigational agents (including monoclonal antibodies) within 6 months (24 weeks) prior to the Screening Visit
- f. Subjects who meet criteria for C-SSRS Suicidal Ideation Items 4 or 5 within the last 12 months prior to screening, OR subjects who endorse any of the 5 C-SSRS Suicidal Behavior Items (actual attempt, interrupted attempt, aborted attempt, preparatory acts, or behavior) within the last 10 years prior to screening, OR subjects who, in the opinion of the Investigator, present a serious risk of suicide (See [Section 6.3.5](#)).

- g. Previous enrollment in any multiple dose BHVS3000 (rimegepant) (PF-07899801) study, such as BHVS3000-201, BHVS3000-305, BHVS3000-404, BHVS3000-405, or BHVS3000-407, regardless of the number of doses taken. Subjects may be considered for BHVS3000-406 (C4951004) if the subject participated in any of the following single dose studies: BHVS3000-301, BHVS3000-302, BHVS3000-303, but did not participate in any multiple dose rimegepant study. Note that subjects who were considered screen failures in a past BHVS-3000 (PF-07899801) study may be considered after discussion with the Sponsor and written approval is received.
- h. Participation in any other investigational clinical trial while participating in this clinical trial.
- i. Past participation in a clinical study within 30 days prior to the Screening Visit.
- j. Failure to complete the Baseline Visit within the timeframe specified in the schedule of assessments.
- k. The subject is, in the investigator's opinion, considered to be otherwise clinically unsuitable for participation in the study including inability to complete the eDiary independently, (the reason for exclusion should be documented in the subject's source file).
- l. Investigator site staff directly involved in the conduct of the study and their family members, site staff otherwise supervised by the investigator, and sponsor and sponsor delegate employees directly involved in the conduct of the study and their family members.
- m. For Germany only: Subjects who are compulsorily detained for treatment of either a psychiatric or physical (e.g., infectious disease) illness (refer to [Section 16.7.2](#)).

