5.5.2. Acute Migraine Medications

Acute migraine medications are those agents recognized as having efficacy in the treatment of acute migraine. Permitted acute migraine medications are presented in Section 16.3, Appendix 3.

Subjects are to keep track of all concomitant medications including acute migraine medications (*used for non-rescue purposes only*, see Section 6.4.4), throughout the course of the study, on an IRB-approved Concomitant Medication paper diary.

Subjects are allowed to use permitted acute migraine medications (see Section 16.3, Appendix 3), as needed, for the treatment of migraine attacks of mild or no headache pain intensity.

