5.7. Deviation from Inclusion/ Exclusion Criteria

Any significant event that does not comply with the inclusion / exclusion criteria, study conduct, or study procedures will be documented as a deviation. Deviations will be documented and reported through the clinical monitoring of the trial. Deviations will be reported to the IRB/EC at the frequency required by your IRB/EC. Prospective approval of protocol deviations to recruitment and enrollment criteria, also known as protocol waivers or exemptions, is not permitted.

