16.3. APPENDIX 3 – Permitted Acute Migraine (Rescue) Medications

- Simple analgesics:
 - Non-steroidal anti-inflammatory drug, including, but not limited to:
 - Aspirin, Ibuprofen, Naproxen
 - Low dose aspirin use for cardiovascular prophylaxis is permitted during the course of this study.
 - Paracetamol (acetaminophen) and paracetamol-containing products (e.g., paracetamol/aspirin/caffeine, etc.)
 - Paracetamol (acetaminophen) and paracetamol-containing products, for the treatment of headache indications, are permitted up to a maximum dose of 2,000 mg of paracetamol per calendar day, up to a maximum of 2 consecutive days at a time (i.e., if administer paracetamol 2,000 mg/day, only allowed to do this on 2 consecutive days at a time)
 - Antiemetics, including but not limited to:
 - Metoclopramide
 - Promethazine
 - Other:
 - Baclofen
 - Other approved pharmacological treatment with established efficacy in the acute treatment of migraine, including locally-recognized standard of care, unless otherwise specified (See [Section 16.2](#), [Appendix 2](#))

These are the only acute migraine medications allowed for rescue treatment at ≥ 2 hours postdose study drug and after completing the 2-hour eDiary entry.

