- **d Cardiovascular Events, Conditions, and Procedures** - Cardiovascular events, conditions, and procedures considered contraindications to the use of triptan medications. Within the current protocol, eligible subjects with any of the following events, conditions, or procedures (as confirmed by information within the medical record) will be included within the study's "CV Subgroup" for the purposes of stratification and subgroup analysis
 - Events:
 - Myocardial infarction (MI)

- Cerebrovascular accident (CVA; e.g., Intracerebral hemorrhage, Intracranial hemorrhage, Subarachnoid hemorrhage, Ischemic stroke, etc.)
 - Prior cardiac arrest
 - Transient ischemic attack(s) (TIA)
- Conditions:
 - Angina pectoris (myocardial ischemia)
 - Cardiac conduction disorder (e.g., Wolff-Parkinson-White [WPW], other life-threatening arrhythmia/heart block)
 - Coronary artery vasospasm (Prinzmetal's angina)
 - Ischemic coronary artery disease (CAD)
 - Ischemic bowel disease
 - Peripheral artery disease (including claudication)
- Procedures:
 - Angioplasty (with or without stent placement)
 - Coronary artery bypass grafting (CABG)
 - Carotid endarterectomy

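### Exclusions 6a and 6g, as written, bar daily low-dose aspirin users in the 3 months before Screening, although Appendix 3 permits the same use on study

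*Protocol*

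**What the plan says.** **Exclusion 6a (Protocol Section 5.3).** The excluded use is "Non-Narcotic Analgesics (e.g., nonsteroidal anti-inflammatory drugs [NSAIDs], paracetamol [acetaminophen], gabapentin, etc.) taken" on 15 or more "days per month for a non-headache indication during the 3 months (12 weeks) prior to the Screening Visit". No exception is given for aspirin.

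**Exclusion 6g (Protocol Section 5.3).** This begins "Permitted acute migraine medication taken" and continues with the same 15-day threshold, the same non-headache condition and the same 3-month look-back. It refers to Section 5.5.2, which states: "Permitted acute migraine medications are presented in Section 16.3, Appendix 3". It also has no exception.

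**Appendix 3 (Section 16.3).** Under the entry "Non-steroidal anti-inflammatory drug, including, but not limited to", the first drug named is aspirin, with no dose stated. The next item reads: "Low dose aspirin use for cardiovascular prophylaxis is permitted during the course of this study".

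**Appendix 1 (Section 16.1).** The on-study restrictions repeat the 15-day rule for non-narcotic analgesics used for non-headache indications, under an opening proviso that gives way to exceptions stated elsewhere.

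**Section 5.7.** "Prospective approval of protocol deviations to recruitment and enrollment criteria, also known as protocol waivers or exemptions, is not permitted".

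**The concern.** Daily low-dose aspirin is a plausible long-term treatment for many of the patients who qualify for the CV stratum. Appendix 4, note d, includes myocardial infarction, ischemic stroke, transient ischemic attack, ischemic coronary disease, peripheral artery disease, angioplasty and coronary bypass. Exclusion 2j removes those whose disease is uncontrolled, unstable or recent, so the patients who remain are mainly stable ones.

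If 6a and 6g catch prophylactic aspirin, a site that follows Section 5.3 to the letter screen-fails these patients. A site that infers an exception from Appendix 3 enrolls them. Eligibility then depends on the reader.

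CV history is the only randomization factor, the stratification variable of the primary analysis, and the subgroup in exploratory objective 17. Losing aspirin users selectively would change the population that subgroup describes. Members of the stratum who do not take aspirin on 15 or more days a month are not affected.

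The reporting would show only part of this. Screen-failure reasons are tabulated (SAP Section 6.2.3.1), but the table does not undo the selection. The SAP's list of relevant protocol deviations (Section 9.1) has no category for NSAID or aspirin use on 15 or more days a month. An aspirin user enrolled against 6a or 6g would therefore not appear there. Such a case would be listed only if it were recorded as a major deviation in the clinical trial management system (SAP Section 6.2.4.2).

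**Working it through.** This is mainly a reading check, with a little arithmetic for scale.

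**Does daily prophylactic aspirin meet the criteria?**

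| Element | 6a | 6g | Daily low-dose aspirin for CV prophylaxis |
|---|---|---|---|
| Drug | Non-narcotic analgesics, NSAIDs named | Any drug on the Appendix 3 list | Listed in Appendix 3 as an NSAID |
| Frequency | 15 or more days a month | 15 or more days a month | 28 of 28 days |
| Indication | Non-headache | Non-headache | Cardiovascular |
| Period | 3 months (12 weeks) before Screening | Same | 3 × 28 = 84 of 84 days |
| Exception | None | None | – |

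Every element is met under both criteria.

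**Does the Appendix 3 allowance rescue the patient?** Its wording covers the course of the study. The look-back in 6a and 6g ends at the Screening Visit, so the two periods do not overlap.

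**Is the on-study rule also in conflict?** No. Appendix 1 yields to exceptions stated elsewhere, and Appendix 3 states one. The gap is confined to the eligibility criteria, which have no such proviso.

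**The plan's power figure (background).** The inputs from Protocol Section 9.1 are 57.9% versus 43.9%, 270 evaluable per arm, and 2-sided alpha 0.05.
- Pooled rate: (0.579 + 0.439)/2 = 0.509
- Null SE: √(2 × 0.509 × 0.491/270) = 0.0430
- Alternative SE: √((0.579 × 0.421 + 0.439 × 0.561)/270) = 0.0426
- z = (0.140 − 1.96 × 0.0430)/0.0426 ≈ 1.31, giving power of 0.904

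This reproduces the stated value of approximately 90%. It does not change materially if the places of excluded aspirin users are refilled.

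**Size of the CV stratum.**
- Cap: 0.15 × 600 = 90 randomized
- Evaluable at the planned 90%: 0.90 × 90 = 81, or 40.5 per arm
- 95% CI half-width for the subgroup difference at the planning rates: 1.96 × √((0.579 × 0.421 + 0.439 × 0.561)/40.5) = 0.216, about 22 percentage points

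The subgroup estimate is imprecise even with the stratum full, so the issue is who is in it rather than its precision.

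**How many could be affected?** The documents give no figure for daily aspirin use. As an assumption only, shares of 25%, 50% and 75% of a full stratum of 90 would be 22.5, 45 and 67.5 places.

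**The case against.** The other side has several fair points.

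- **Low-dose aspirin may not be an analgesic.** The governing term in 6a is analgesics, and antiplatelet-dose aspirin is not taken as one. This has some force against 6a. It does not touch 6g, which never uses that term and turns on membership of the Appendix 3 list.
- **Section 5.5.2 defines acute migraine medications by efficacy in acute migraine.** A site might argue that prophylactic-dose aspirin falls outside that class. However, the definition speaks of agents, Appendix 3 names aspirin without a dose, and the non-headache wording in 6g makes sense only for listed drugs used for some other purpose.
- **The aspirin allowance lies on 6g's own reference path.** A reader who follows 6g to Appendix 3 finds it beside the word aspirin. That shows intent, since an on-study allowance has little use if established daily users cannot enroll. It does not supply the exception, because its wording is limited to the study period, and 6a has no link to it.
- **Sites can ask.** A medical monitor is available (Protocol Section 10.8), and the sponsor has issued clarification letters on this study. Interpretation is not waiver, so a uniform answer is possible. It would depend on every site asking, and it leaves the criterion unchanged.
- **The consequences are limited.** The criteria act before randomization, so the treatment comparison is not biased. The CV subgroup analysis is exploratory and its p-values are descriptive. The stratum also includes conditions with no evident link to daily aspirin, such as Wolff-Parkinson-White syndrome and intracranial hemorrhage. All of this stands, and it bounds the importance of the point.

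**Conclusion.** The concern holds. Read as written, 6a and 6g exclude patients on daily prophylactic aspirin before Screening, while Appendix 3 shows that the protocol means such patients to take part. The case is clearest under 6g, which reaches aspirin by name through the Appendix 3 list.

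The size is modest. The affected patients fall mainly in a stratum of at most 90 randomized subjects, in an unknown number. Any under-representation assumes that at least some sites apply the strict reading, which the documents neither show nor rule out. Type I error, the primary analysis and the validity of the randomized comparison are untouched. Primary power stays at about 90% provided excluded places are refilled. What remains is inconsistent eligibility and a CV subgroup that may not represent aspirin-treated patients. That is worth correcting but does not threaten the primary result.

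**What to change.** Add to both 6a and 6g in Protocol Section 5.3: *except low-dose aspirin for cardiovascular prophylaxis*. For consistency, the same words can go in the Appendix 1 item on non-narcotic analgesics, although its opening proviso already covers the case.

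The cost is one clause in each of two criteria. Section 12 requires permanent changes to go through an amendment, so the clauses belong in one. No new data, procedures or analyses are needed.
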